TITLE: ASSESSING VENTILATOR SAFETY IN PATIENTS ON PRESSURE SUPPORT VENTILATION

Short Title: ASOP

Duke IRB # Pro00106860

ClinicalTrials.gov: NCT05125952

Clinical Protocol Synopsis

1. Title

Assessing Ventilator Safety in Patients on Pressure-support Ventilation (ASOP)

2. Background

Ventilator-induced lung injury (VILI) is known to cause significant morbidity and mortality in patients with acute respiratory failure.¹ Lung injury caused by large tidal volumes (“volutrauma”), high pressures (“barotrauma”), repetitive airway collapse (“atelectrauma”), and large changes in transpulmonary pressure during a breath (“driving pressure”) are all known to cause VILI.² Most studies on VILI have involved the effects of inappropriate (often excessive) mechanical ventilator settings. More recently, it has been noted that similar lung damage can be caused by large, patient generated, uncontrolled tidal volumes and driving pressures, which has been termed “self-induced lung injury,” or SILI^{3,4}. These patient generated large tidal volumes may be disease induced (e.g. neurologic injury) or be driven by other factors (e.g. metabolic derangements, anxiety). Importantly, interactions of patient efforts with assisted/supported modes of mechanical ventilation may worsen this.

Pressure-support ventilation (PSV) is a common mechanical ventilation mode often used in patients with active inspiratory efforts to help reduce patient inspiratory work and improve comfort. PSV effectively allows spontaneously breathing patients to determine their breath flow-rate and breath duration, eliminating flow and cycle dyssynchrony.⁵ However, pressure support ventilation does not allow for physicians to control tidal volume or driving pressure. The risk of SILI may thus be increased with PSV.

Assessing SILI risk during PSV should involve more than just measuring the delivered tidal volume and should also include the end inspiratory alveolar pressure (plateau pressure or Pplat) and the airway driving pressure (DP = Pplat-PEEP). However, these are difficult to assess during PSV. Several different methods have been proposed to address these challenges⁷⁻⁹. However, to date none of these methods have been compared to assess for concordance in their ability to indicate an increased risk of self-induced lung injury.

3. Focus of the Study and Specific Aim.

ASOP is a prospective cohort study comparing three methods for assessing risk of self-induced lung injury in patients with acute respiratory failure being managed with pressure-support ventilation.

Specific Aim: We will describe the relationship between three different assessment methods for risk of self-induced lung injury and compare them to a gold standard measurement. The “gold standard” for SILI risk will be a direct assessment of transpulmonary Pplat and DP using an esophageal balloon tipped catheter to measure esophageal pressure (Pes) as a surrogate for pleural pressure. We will compare these to three assessment techniques using only the conventional airway pressure monitor: a plateau pressure and DP calculation in pressure support ventilation, an airway occlusion test in pressure support ventilation, and a plateau pressure and

DP calculation in volume-control ventilation in each patient. Our central hypothesis is that these three techniques will give similar results to “gold standard”.

4. Study Population

Inclusion Criteria:

- Adult patients (≥ 18) with acute respiratory failure receiving invasive mechanical ventilation
- Managed in pressure-support mode of ventilation

Exclusion Criteria:

- Actively undergoing a spontaneously awakening trial or SAT
- Patient or surrogate is unable to provide informed consent
- Currently pregnant
- Currently incarcerated
- Acute exacerbation of an obstructive lung disease
- Known esophageal varices or any other condition for which the attending physician deems an orogastric catheter to be unsafe
- Esophageal, gastric or duodenal surgical procedures within the last 6 months

5. Screening and Recruitment

Study staff will identify potentially eligible patients during the study period using medical records and lists maintained for clinical operations. If a potentially eligible patient is identified, their clinical team will be contacted to ensure that the patient is appropriate for inclusion in the study. If deemed appropriate for participation by the clinical team, the LAR will be approached for consent.

6. Process of obtaining informed consent

A member of the study team will obtain permission from the legally authorized representative for each patient. It is necessary to obtain consent from the LAR in the study population as these individuals will be sedated and on mechanical ventilation. However, once the subject becomes capable of giving consent, the study team will approach them for study re-consent. We will obtain consent via paper consent.

Paper consent process

1. The informed consent document is provided to the patient's LAR.

2. Research staff discuss the informed consent document with the LAR in person. This step confirms subject/LAR identity.
3. If the LAR decides to consent to participate, the LAR signs the informed consent document.
4. Research staff signs consent document confirming their participation in the informed consent process.
5. A copy of the consent is provided with two copies of the consent, one for the LAR and one for participant.
6. Original signed consent is stored in study folder. A copy of the signed consent is uploaded to EHR.

7. Data collection

All data will be collected by study staff either through review of electronic health record or via direct measurements at the patient bedside after study enrollment.

Data collected from the electronic health record at enrollment will include:

- Baseline sociodemographic data
- Admission height and weight
- Admission diagnosis
- Duration of mechanical ventilation prior to study enrollment
- APACHE II Illness score

Data collected at the patient bedside will include:

- Baseline ventilator variables including
 - PEEP
 - Pressure support above PEEP
 - Fraction of inspired oxygen (FiO₂)
 - Tidal Volume
- Study specific measurements
 - Transpulmonary plateau pressure during a volume control breath
 - Transpulmonary driving pressure during a volume control breath
 - Airway plateau pressure during a volume-control breath
 - Airway driving pressure during a volume-control breath
 - Airway plateau pressure during a pressure-support breath
 - Airway driving pressure during a pressure-support breath
 - Transpulmonary plateau pressure during a pressure support breath
 - Transpulmonary driving pressure during a pressure support breath
 - Airway plateau pressure during a pressure-support breath measured using a Resironics NM3 device
 - Airway driving pressure during a pressure-support breath measured using a Resironics NM3 device

- Dynamic change in airway pressure (“occlusion pressure”) and transpulmonary pressure during an airway occlusion maneuver during a pressure support breath
- Respiratory effort as measured by the ventilator p(0.1).
- Change in tidal volume with a decrease in set pressure-support
- Change in airway and transpulmonary plateau pressure with decreased pressure support
- Change in airway and transpulmonary driving pressure with decreased pressure support

Data collected from the EHR after study specific measurements will include

- Total duration of mechanical ventilation in days
- Total duration of intensive care length of stay in days
- Total duration of hospital length in stay in days
- Survival to discharge

No data will be collected after the patient is discharged from the hospital.

8. Randomization

This is a cohort study and there will be no randomization of patients to a treatment or control. Due to possible bias based of order of methods assessed, we will randomize the order that each patient is tested, including the gold standard (A) and the three methods of interest (B, C and D). Randomization schema will be a simple randomization of the methods for each patient, where each patient will be assessed on all 4 methods. A list of method order will be created prior to study start with order consisting of (e.g. ABCD, BCDA, CDAB, etc).

9. ASOP procedures.

ASOP is a prospective cohort study comparing three methods for assessing risk of self-induced lung injury to a gold-standard measurement in patients with acute respiratory failure being managed with pressure-support ventilation.

The study will compare the following four methods for assessing risk for SILI during PSV:

1. The transpulmonary plateau and driving pressure during a volume control. This will be considered the gold standard measurement of both plateau and driving pressure.
2. The airway plateau and driving pressure during a volume control breath.
3. The airway plateau and driving pressure during a pressure support breath
 - a. This variable will be measured in two ways. Once using an inspiratory hold on the Servo ventilator, and once using a Resironics NM3 device with VentAssist SoftWare.
4. The dynamic change in airway pressure and transpulmonary pressure during an end expiratory occlusion maneuver during a pressure support breath.

After enrollment, all baseline ventilator settings will be recorded (including PEEP, pressure support, tidal volume, and FiO2).

The patient will then be transitioned to a study ventilator with software needed to measure esophageal and transpulmonary pressure. A Resironics NM3 device with VentAssist software will be connected to the ventilator. With this ventilator, an inspiratory hold can be performed in pressure support ventilation, so a plateau pressure (P_{plat}) and driving pressure (DP) in PSV mode will be recorded. For all measurements with an esophageal balloon, an orogastric catheter fitted with esophageal balloon will be placed, with placement validated using previously described techniques.⁶ Flow cycling will be set to the minimal value.

The following study procedure will be followed for each patient participating (note: variable numbers correspond to those in research data form).

- 1) Record baseline demographic and clinical data in study data sheet.
- 2) Record baseline ventilator data in study data sheet
 - a) Baseline PEEP
 - b) Baseline Pressure support
 - c) Baseline FiO_2
 - d) Baseline Respiratory rate
 - e) Baseline Tidal volume
 - i) Record 5 measurements in data sheet, calculate mean
- 3) Determine study maneuver order (from predetermined randomization of maneuvers).
- 4) Insert esophageal pressure catheter and confirm placement by Baydur maneuver. Attach NM3 device. Set flow cycling to the minimum amount.
- 5) Perform following maneuvers in predetermined order, and record associated variables/measurements. All measurements to be done with PEEP, PS, and FiO_2 the same as baseline reading in section 2 as above.
 - a) Static respiratory system driving pressure ($DPrs$), respiratory system driving pressure as measured by NM3 monitor ($DPrs-NM3$), and transpulmonary driving pressure (DP_{tp}) and $p(0.1)$ using inspiratory hold in pressure-support ventilation
 - i) Record PEEP from ventilator(a.1)
 - ii) Record PEEP from NM3 monitor (a.2)
 - iii) Record end expiratory esophageal pressure (a.3)
 - iv) Perform inspiratory hold
 - (1) Measure airway plateau pressure (a.4)
 - (2) Measure end-inspiratory esophageal pressure (a.5)
 - v) Record plateau pressure as measured from NM3 monitor (a.6)
 - vi) Repeat for 5 total measurements of each variable
 - vii) Calculate respiratory system driving pressure from ventilator ($a7 = a.4 - a.1$) for each recorded breath
 - viii) Calculate respiratory system driving pressure from NM3 ($DPrs-NM3$) monitor ($a.8 = a.6-a.2$)

- ix) Calculate transpulmonary driving pressure from ventilator and esophageal balloon ([a.4-a.5]-[a.1-a.3]) for each recorded breath
- x) Record P(0.1) from ventilator for 5 breaths (a.10)

b) Measure dynamic respiratory system driving pressure (DPrs-dyn) and transpulmonary driving pressure (DPtp-dyn)

- i) Record PEEP from ventilator (b.1)
- ii) Record PEEP from NM3 monitor (b.2)
- iii) Record end-expiratory esophageal pressure during a breath (b.3)
- iv) Record maximum airway pressure (b.4)
- v) Record maximum inspiratory esophageal pressure (b.5)
- vi) Record Airway plateau pressure from NM3 monitor (b.6)
- vii) Repeat for 5 total measurements of each variable
- viii) Calculate dynamic driving pressure across the respiratory system (DPrs-dyn) (b.7 = b.4-b.1)
- ix) Calculate dynamic transpulmonary driving pressure (DPtp-dyn) (b.8 = ([b.4-b.5]-[b.1-b.3]))
- x) Calculate the dynamic driving pressure across the respiratory system from the NM3 monitor DPrs-Dyn-NM3 (b.6-b.2)

c) Measure airway occlusion test (AOC)

- i) Measure PEEP (c.1)
- ii) Measure end expiratory esophageal pressure (c.2)
- iii) Perform expiratory hold
 - (1) Expiratory hold should be held for entirety of respiratory effort until airway pressure returns to baseline
 - (a) Measure maximum negative deflection of airway pressure (c.3)
 - (b) Measure maximum negative deflection of esophageal pressure (c.4)
- iv) Repeat 5 total measurements of each variable
- v) Calculate airway occlusion pressure (AOC = c.1-c.3) for each breath

d) Measure static respiratory system (DPrs-vc) and transpulmonary driving pressure (DPtp-vc) in volume control breath

- i) Change ventilator mode to SIMV (PSV+VC), with IMV breaths set in Volume control.
 - (1) Set PSV settings identical to baseline settings recorded in section 2.
 - (2) For VC breaths, volume set to average tidal volume calculated in section 2. subsection D.
 - (3) Set rate of IMV breaths to 1/min
 - (4) Set flow rate for VC breaths to minimum
- ii) Measure PEEP (d.1)
- iii) Measure end-expiratory esophageal pressure (d.2)
- iv) Measure airway plateau (d.3) during inspiratory hold
- v) Measure end-inspiratory esophageal pressure (d.4) during inspiratory hold
- vi) Repeat for 5 total measurements of each variable
- vii) Calculate respiratory system driving pressure (DPrs-vc = d.2-d.1)
- viii) Calculate transpulmonary plateau pressure (d.6 = d.2-d.4)

- ix) Calculate driving pressure across the lung ($DP_{tp-vc} = d.6 - (d.1-d.3)$)
- e) Measure change in airway plateau pressure and patient effort with decrease in Pressure-support.
 - i) Ventilator will be returned to baseline settings
 - ii) The set pressure support will be decreased by 5 cm of H₂O (to a minimum of 5 cm of H₂O)
 - iii) The new tidal volume will be recorded (e.1)
 - iv) Measure PEEP (e.2)
 - v) Measure end-expiratory esophageal pressure (e.3)
 - vi) Perform and inspiratory hold in pressure-support
 - (1) Measure airway plateau pressure (e.4)
 - (2) Measure end-inspiratory esophageal pressure (e.5)
 - vii) Measure a P(0.1) (e.6)
 - viii) Repeat for 5 total measurements of each variable
- ix) Calculate new static respiratory system driving pressure (DP_{rs-new}) (e.7=e.4-e.2)
- x) Calculate new transpulmonary driving pressure (DP_{l-new}) (e.8=[e.4-e.5]-[e.2-e.3])
- f) Return all ventilator settings to baseline.

The order of performing these measurements will be randomized to minimize bias of the order of measurements.

All study specific measurements and maneuvers will be completed in one day. After completion of study measurements and maneuvers, the orogastric balloon will be removed.

A patient's EHR will be monitored until hospital discharge to collect previously mentioned study specific endpoints as described above.

Overall, we plan to enroll 25 patients.

10. Statistical design, analyses, sample size, and power

Statistical Design and Analysis Plan

Patient and clinical characteristics will be described overall using frequency and percent for categorical characteristics, and mean, standard deviation, median, and quartiles for continuous variables. Agreement statistics such as the intraclass correlation coefficient (ICC), Bland-Altman plots, and Cohen's kappa, will be used to assess agreement of measures between the gold-standard and the three methods of interest. A mixed-effects regression model will be used to determine the difference between each method and the gold-standard taking into account the randomization order with results presented as the least squares mean (LSM) difference with 95% confidence interval (CI). All analyses will be performed using SAS 9.4 (Cary, NC) and a p-value <0.05 will be considered statistically significant.

Sample Size and Power

This is a descriptive study. The 25-person sample size reflects the pragmatics of recruitment with available study staff and should provide adequate power to evaluate similarities given that each patient acts as his/her own control.

11. Subject Participation and Duration

Study specific measurements will take one day to complete. Patients will be followed until their discharge from the hospital.

12. Study Duration

We estimate that from the time enrollment opens it will require 1 year to complete all study activities.

13. Costs to the Subject

There are no costs to participants.

14. Compensation

There is no compensation for participation in this study.

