## 1.4 Statistical Analysis Plan

### 1.4.1 Demographic and Clinical Characteristics (“Table 1”)

The variables listed in Section 3.2 will be summarized for the cohort using mean with standard deviation, median with 25th and 75th percentiles (Q1, Q3), and min-max for continuous measures, and frequency with percentage for categorical measures.

### 1.4.2 Analyses Plan for Aim 1

The internal consistency of the static respiratory driving pressure (DPRS), that is to say the consistency of DPRS measures from the same patient, will be quantified for each maneuver (A, B, C, and D) separately using the intraclass correlation coefficient (ICC). The ICC measures the correlation of two observations coming from the same patient.

Specifically, the ICC is defined as

$$ICC = \frac{\sigma_{\alpha}^2}{\sigma_{\alpha}^2 + \sigma_{\epsilon}^2}$$

Where  $\sigma_{\alpha}^2$  is the variation in DPRS measurements between different patients, and  $\sigma_{\epsilon}^2$  gives the within-patient variation of DPRS measurements, with the sum  $\sigma_{\alpha}^2 + \sigma_{\epsilon}^2$  giving the total variation in DPRS values across all patients. Therefore, the ICC measures the proportion of total variation in the DPRS measurements that is due to variation between patients.

95% confidence intervals for each of the within-patient and between-patient variances, as well as the ICC, will be calculated using the empirical 2.5th and 97.5th percentiles of 10,000 parametric bootstrap replications.

General guidelines for interpretation of ICC values are as follows (Cicchetti, 1994):

- <0.40: poor consistency
- 0.40-0.59: fair consistency
- 0.60-0.74: good consistency
- 0.75-1.00: excellent consistency

Technical details:

The values of  $\sigma_{\alpha}^2$  and  $\sigma_{\epsilon}^2$  will be estimated from a linear mixed-effects model, with

$$Y_{ij} = \mu + \alpha_i + \epsilon_{ij}$$

With  $Y_{ij}$  being the  $j$ th DPRS measurement from the  $i$ th patient, with up to 5 measurement each from the 15 patients enrolled.

Here, the underlying mean DPRS value is  $\mu$  and the subject-specific deviation from the overall mean is given by  $\alpha_i$  for the  $i$ th patient, and the within-patient variation of measurements is given by  $\epsilon_{ij}$ .

We assume that

$$\alpha_i \sim N(0, \sigma_\alpha^2), \epsilon_{ij} \sim N(0, \sigma_\epsilon^2)$$

With  $\alpha_i$  and  $\epsilon_{ij}$  each iid and independent of each other.

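### The order list has no required balance and its eligible orders are not stated, and the SAP drops the order term that the protocol promised

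*Protocol*

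**What the plan says.** Protocol section 8 gives its reason for ordering: "Due to possible bias based of order of methods assessed, we will randomize the order that each patient is tested". The method is "Randomization schema will be a simple randomization of the methods for each patient, where each patient will be assessed on all 4 methods", and the list is described by example: "A list of method order will be created prior to study start with order consisting of (e.g. ABCD, BCDA, CDAB, etc". The items to be ordered are the four methods, "including the gold standard (A) and the three methods of interest (B, C and D". No block, position balance or predecessor balance is asked for.

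Protocol section 9, step 5, is organised differently. It lists maneuvers a to e. Step 5d is headed "Measure static respiratory system (DPrs-vc) and transpulmonary driving pressure (DPtp-vc) in volume control breath", so the gold standard and the airway volume-control method come from the same breaths. After steps e and f the section says again that the order of the measurements is randomised, without saying whether e is included.

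Protocol section 10 plans a mixed-effects model of each method against the gold standard that allows for the randomised order. SAP sections 1.4.2 and 1.4.3 have terms for patient, method, patient by method, and residual. They have none for order, position or predecessor, and the variable lists in SAP section 1.3 contain no order variable.

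On size, the protocol says "Overall, we plan to enroll 25 patients", while SAP section 1.4.2 works "with up to 5 measurement each from the 15 patients enrolled". SAP section 1.2.3 dates the dataset February 22, 2024.

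**The concern.** The protocol treats order as a possible source of bias and randomises to deal with it. How well that works depends on two things the text leaves open: which orders can be drawn, and whether position and predecessor are balanced over a very small number of patients.

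The examples add to the doubt. ABCD, BCDA and CDAB are the same sequence started at different points. A list built only from such rotations balances position, but B can follow only A, C only B, D only C and A only D. A lingering effect of one maneuver on the next would then be hard to separate from a difference between methods.

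The analysis is the second safeguard, and the SAP leaves it out. In the SAP's pairwise model, a position or carry-over effect that differs between patients because their orders differ goes into the patient-by-method term. That lowers the interclass correlation. A constant effect goes into the method term, which that correlation excludes but which shifts the mean difference in the Bland-Altman plot of maneuvers A and D.

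**Working it through.** The documents give no figure for the order list, and the planned size has a practical basis ("The 25-person sample size reflects the pragmatics of recruitment with available study staff"), so there is no stated figure to reproduce. The check compares three lists at the two sizes in the documents, n = 15 (SAP) and n = 25 (protocol).

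**1. Predecessor pairs.** Four items have 4 × 3 = 12 ordered predecessor pairs, and each order of four contains 3 adjacent pairs.
- Four rotations (ABCD, BCDA, CDAB, DABC): 4 × 3 = 12 adjacencies, falling on only 4 distinct pairs, 3 times each. The other 12 − 4 = 8 never occur.
- All 24 orders: 24 × 3 = 72 adjacencies, 72 / 12 = 6 per pair.
- Williams square (for example ABDC, BCAD, CDBA, DACB): 12 / 12 = 1 per pair.

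**2. Variance of a method difference.** The model has one value per patient and method (the mean of its breaths) with residual variance σ²:

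value = patient + position + method + carry-over from the previous method + error.

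The variance of a contrast c is c′(X′X)⁻¹c · σ², averaged over pairs. With nothing lost it would be 2σ²/n, that is 0.133 at n = 15 and 0.080 at n = 25. Results are in units of σ²; the simple-randomisation row is an average over simulated lists and moves by about 0.001 between runs.

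| List | Carry-over fitted, n = 15 | n = 25 | Position only, n = 15 | n = 25 |
|---|---|---|---|---|
| Rotations only | 0.745 | 0.442 | 0.134 | 0.080 |
| Simple randomisation over 24 orders | 0.173 | 0.096 | 0.144 | 0.083 |
| Williams | 0.148 | 0.088 | 0.134 | 0.080 |

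- Rotations against Williams, carry-over fitted: 0.745 / 0.148 = 5.0 and 0.442 / 0.088 = 5.0. Position only: 1.00 at both sizes.
- Simple randomisation against Williams, carry-over fitted: 0.173 / 0.148 = 1.17 and 0.096 / 0.088 = 1.09. In standard error this is √1.17 = 1.08 and √1.09 = 1.04. Position only: 0.144 / 0.134 = 1.08 and 0.083 / 0.080 = 1.04 in variance.

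Even for rotations the model can be estimated. At n = 24 it has 24 + 3 + 3 + 3 = 33 columns and rank 33, because first-position readings have no predecessor.

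**3. Bias if carry-over exists and is not fitted.** Take a carry-over of 1 unit from D (an assumption, used only for scale).
- Rotations: A follows D in 3 of 4 orders, so every contrast with A shifts by −0.75.
- All 24 orders in equal numbers, or Williams: A, B and C each follow D in a quarter of orders (6 / 24 = 0.25). B − A and C − A do not shift; D − A shifts by −0.25.
- Simple randomisation: the same averages, with a standard deviation for B − A and C − A of about 0.18 at n = 15 and 0.14 at n = 25.

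**4. Chance imbalance in position.** Under simple randomisation over 24 orders, a given pair of methods differs in mean position by more than half a place in about 29% of lists at n = 15 and 17% at n = 25.

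**5. What is compared and where it is measured.**
- Protocol gold standard against airway volume control: both from maneuver d, so order cannot affect the contrast.
- SAP A (inspiratory-hold driving pressure) and B (P0.1): both recorded in protocol maneuver a.
- SAP C: combines readings from protocol maneuvers b and c.
- SAP D: protocol maneuver d.

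Of the SAP's six pairs, AB has no maneuver order. AD and BD compare a with d. AC, BC and CD involve a quantity measured at two positions.

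**The case against.** The strongest reply is that the protocol specifies simple randomisation of the methods and gives rotations only as open-ended examples. Read literally, all 24 orders are eligible and no method has a fixed predecessor. This stands. A reader might infer from the examples that each method always follows the same one, so that carry-over is confounded with method. The text does not support that, and the 5-fold figure applies only if the list was in fact confined to rotations. Even then the confounding is partial, and a balanced set of rotations is as efficient as a Williams list when only position is adjusted for.

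The loss under the literal reading is modest: 4% to 8% in standard error with carry-over fitted. The protocol also plans an order-adjusted model. Both are true, but that model does not appear in the SAP.

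Carry-over is an assumption. Step 5 keeps PEEP, pressure support and FiO2 at baseline, and no document gives a size or shows an effect. This limits the point to a property of the design. It does not rule carry-over out: step 5d changes the ventilator mode, the return to baseline is written only in e and f, the baseline rule does not mention mode, and no interval between maneuvers is given.

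Finally, the variances assume four separately ordered items, which neither document's comparisons match exactly. That stands too. They compare lists and do not forecast the precision of any planned contrast.

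**Conclusion.** The point holds as a minor one. The protocol does not say which orders are eligible and asks for no balance, and the SAP omits the order adjustment that the protocol promises.

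- If all 24 orders are eligible, there is no systematic confounding. The cost against a Williams list is about 17% in variance at n = 15 and 9% at n = 25 with carry-over fitted, or 8% and 4% with position only.
- If only rotations were used, method and first-order carry-over are partially but severely confounded, with about 5 times the variance of a Williams list after carry-over adjustment and no loss with position only.

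These figures assume one value per patient and method, constant residual variance, carry-over reaching only the next maneuver, and four separately ordered items. They do not show that any result is biased. Nor would a balanced list remove bias from an unfitted carry-over: a shift of a quarter of the carry-over remains in contrasts with the maneuver that causes it.

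The firmest part needs no assumption about carry-over: the labels in section 8 cannot all be ordered independently, and the SAP has no order term.

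**What to change.** For the SAP, which is where a change can still take effect:
- Add the realised order to the variable list in section 1.3, and report how often each maneuver fell in each position and followed each other maneuver. This also settles whether the list was confined to rotations.
- In section 1.4.3, add maneuver position as a fixed effect for pairs measured in different maneuvers. It does not apply to AB. For pairs with C, state which position is used, since its parts come from b and c.
- Fit predecessor as a sensitivity analysis, and say that it will be imprecise if the realised orders are all rotations.

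The cost is one variable and a model term. In a pairwise comparison of 15 patients, four positions leave 15 − 1 − 3 = 11 degrees of freedom for the method difference; a linear position term uses one degree of freedom instead of three.

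For the protocol, define the order list on the maneuvers performed rather than on methods A to D, and reconcile section 8 with section 9 on whether maneuver e is randomised. If the list can still be changed, balance it for position and predecessor. For a to d, use a 4-sequence Williams square in randomly permuted blocks of four. If e is included, use the 10-sequence version, in which 10 × 4 = 40 adjacencies cover the 5 × 4 = 20 ordered pairs twice each. Neither 15 nor 25 is a multiple of 4 or 10, so balance will be close rather than exact. This needs no extra patients or measurements.

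### The protocol's only designated gold standard is transpulmonary pressure on a volume-control breath, and neither document compares the PSV airway methods with the PSV transpulmonary pressure already collected

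*Protocol*

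**What the plan says.** **Protocol**

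- Section 9 introduces its list with "The study will compare the following four methods for assessing risk for SILI during PSV". The first item is "The transpulmonary plateau and driving pressure during a volume control" breath, which it makes the gold standard for both quantities. The second, a tested method, is "The airway plateau and driving pressure during a volume control breath". The third is airway pressure on a PSV breath, read by a ventilator hold and by the NM3 device. The fourth is an occlusion maneuver in PSV.
- Section 3 (Specific Aim) defines the gold standard as a "direct assessment of transpulmonary Pplat and DP using an esophageal balloon tipped catheter to measure esophageal pressure (Pes) as a surrogate for pleural pressure" and does not restrict it to a mode.
- Section 2 (Background) gives the motive: "pressure support ventilation does not allow for physicians to control tidal volume or driving pressure".
- Section 7 lists "Transpulmonary plateau pressure during a pressure support breath" among the study measurements, with the matching driving pressure. Section 9, step 5a (ix), reads: "Calculate transpulmonary driving pressure from ventilator and esophageal balloon ([a.4-a.5]-[a.1-a.3]) for each recorded breath". Neither value is designated as a reference.
- Section 9, step 5d, records PEEP, airway plateau and both esophageal pressures in one sequence, repeated five times. The VC volume is set to the mean baseline PSV tidal volume.
- Section 10 applies ICC, Bland-Altman plots, kappa and an order-adjusted mixed model to each method against the gold standard.

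**SAP**

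- Section 1.1.1 gives the gold-standard role to Maneuver A, the airway static driving pressure on a PSV hold.
- Section 1.3.1 lists no esophageal pressure among the maneuver variables.
- Section 1.4.4 plans one Bland-Altman plot, A against D (airway PSV against airway VC).

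**The concern.** The study asks about breaths whose size the patient determines, but the protocol's reference is taken on a breath of machine-set volume. It also comes from the same hold as one of the three tested methods. The methods are therefore not compared with the reference on equal terms. Poorer agreement for a PSV method could arise only because the reference was another breath, in another mode, at another time. A reader of the results could take that as a defect of the PSV method.

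The SAP's different gold standard leaves a second gap. Its analysis has no transpulmonary reference at all, so it cannot address the comparison promised in the Specific Aim.

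**Working it through.** No stated figure bears on this point. The 25 patients in protocol section 10 are justified on practical grounds, without an SD, margin or power value. The check is algebra plus an illustration with assumed SDs.

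**1. Same-breath difference in VC.** I use the quantities of step 5d by name: PEEP, airway plateau (Pplat), end-expiratory and end-inspiratory esophageal pressure (Pes_ee, Pes_ei).

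- Airway driving pressure (DP) = Pplat − PEEP
- Transpulmonary DP = (Pplat − Pes_ei) − (PEEP − Pes_ee)
- Difference = Pes_ei − Pes_ee, the Pes swing

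Pplat and PEEP cancel, and so do their errors. The airway formula printed in step 5d subtracts d.1 (PEEP) from d.2, which is labelled as an esophageal pressure. SAP section 1.3.1 uses airway plateau minus PEEP for Maneuver D, which supports reading the quantities by name. The printed transpulmonary DP, (d.2−d.4)−(d.1−d.3), rearranges to (d.3−d.4)−(d.1−d.2), the form used above.

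**2. Same-breath difference in PSV (step 5a).**

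- Ventilator hold: (a.4−a.1) − {[a.4−a.5]−[a.1−a.3]} = a.5−a.3, again the Pes swing.
- NM3: (a.6−a.2) − {[a.4−a.5]−[a.1−a.3]} = (a.6−a.4) − (a.2−a.1) + (a.5−a.3). The device differences remain.

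**3. Scatter against the VC reference.** Assume two equally accurate airway methods, no true difference between modes, breath error of SD s in each mode, errors independent between modes, a Pes swing of patient-to-patient SD 1 cmH2O with no breath-to-breath variation, and n breaths averaged.

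- Airway VC half-width = 1.96 × 1 = 2.0
- Airway PSV half-width = 1.96 × √(1 + 2s²/n)

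| s (cmH2O) | Airway VC | Airway PSV, n = 5 |
|---|---|---|
| 1 | 2.0 | 1.96 × √1.4 = 2.3 |
| 2 | 2.0 | 1.96 × √2.6 = 3.2 |
| 3 | 2.0 | 1.96 × √4.6 = 4.2 |

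**4. Sensitivity.**

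- With breath error in PSV only, the PSV half-width is 1.96 × √(1 + s²/5) = 2.1, 2.6 and 3.3.
- Pairing single breaths (n = 1, error in both modes) would give 3.4, 5.9 and 8.5, but no document specifies such pairing.
- If the swing itself varied from breath to breath with SD 1, the single-breath VC half-width would rise to 1.96 × √2 = 2.8.

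**5. Correlation.** Take a between-patient SD of airway DP of 3, a swing SD of 1, and an error SD of 1 in each patient's mean. The correlation with the VC reference is 10/√(10 × 11) = 0.95 for airway VC and 9/√(10 × 11) = 0.86 for airway PSV.

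**6. Mean.** Under these assumptions both airway methods differ from the reference by the same mean Pes swing. Sharing a breath does not change the expected mean difference in the mixed model. A true difference between modes, for which the documents give no figure, would enter the PSV difference.

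**7. SAP.** D is compared with A across modes, so the cancellation in step 1 does not occur there. Maneuver C's predicted transpulmonary swing is built from airway pressures only.

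**The case against.** The VC reference can be defended. Protocol section 2 says plateau and driving pressure are hard to assess in PSV, so a reference outside that mode has a rationale. The VC volume is matched to the patient's mean PSV volume, and step 5 holds PEEP at its baseline value. The study is descriptive, hypothesises similarity, and does not plan to rank methods. A PSV reference from step 5a also shares a.4 and a.1 with the ventilator-hold method, so as sole reference it would reverse the advantage and hide errors in the PSV plateau. All of this stands. It argues for keeping the VC reference beside a PSV one, not for leaving the PSV one out.

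A reader might infer stronger claims, which the documents do not support:

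- *The study has no PSV reference.* That is true only of the designation. PSV transpulmonary plateau and driving pressure are collected.
- *The VC method is favoured throughout.* The asymmetry belongs to the protocol's plan. In the SAP, D is compared with a PSV measure.
- *The reference fixes driving pressure.* VC fixes volume; driving pressure is measured.
- *Airway VC must agree with the reference.* The Pes swing remains in full as an offset.

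**Conclusion.** The point holds in this form. The protocol's designated reference is VC-only for a PSV question, although its own aim does not require that. Under the protocol's plan, airway VC has a built-in advantage in limits of agreement, ICC and correlation, but not in mean offset. The direction follows from the algebra whenever errors in the two modes are independent. The size is not known: on five-breath means the illustration ranges from slight (2.0 against 2.3 cmH2O) to about double (2.0 against 4.2), and it rests wholly on assumed SDs.

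The SAP removes that asymmetry but drops the transpulmonary reference. The comparison closest to the study question, PSV airway methods against PSV transpulmonary pressure, is therefore specified in neither document. The collected data are not compromised. The analysis plan should be changed.

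**What to change.** 1. Reconcile the gold standards in protocol section 9 and SAP section 1.1.1.
2. Add to the SAP the step 5a transpulmonary plateau (a.4−a.5) and driving pressure ([a.4−a.5]−[a.1−a.3]) as the mode-matched reference for the PSV ventilator-hold and NM3 methods. Report the occlusion method against it as a same-mode, different-breath comparison.
3. Keep the VC transpulmonary value as the reference for airway VC and as a cross-mode comparison for the PSV methods.
4. State that the airway VC and PSV ventilator-hold same-breath differences in driving pressure reduce to the Pes swing and so do not test plateau accuracy. The NM3 difference does not reduce in this way, because the device supplies its own plateau and PEEP.
5. State that same-breath agreement will not be ranked against cross-mode agreement.

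SAP section 1.2.3 already records a data version and section 1.4.3 mentions discarded measurements. The addition should therefore be dated and made before these comparisons are run.

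No new measurements are needed. The cost is two references to report instead of one, esophageal variables to add to the SAP dataset, and wording changes in both documents.
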